7.3.3. Subgroup Analyses

Subgroups will be formed in the ITT population based on the following prognostic factors, participant characteristics, and baseline variables:

- Age: < 65 years, ≥ 65 years
- Sex: male, female
- Race: White, others
- Region: North America, EU, or Asia
- PD-L1: CPS 1% to 19% or $\geq 20\%$
- HPV p16 status (oropharyngeal only): p16-positive versus p16-negative
- LAG-3 expression status: positive ($\geq 5\%$) or negative ($< 5\%$)
- Number of target lesions (for PFS subgroup analysis only): 1, 2, or 3+

Subgroups may be further divided or combined based on emerging data. If the subgroup size is fewer than 5, then the analysis may not be conducted in this particular subgroup. To determine whether the treatment effect for the primary endpoint of PFS is consistent across various subgroups, the estimated HR and its 95% CIs will be provided within each category of subgroup

using the unstratified Cox regression model. A forest plot will be produced; this will provide the estimated point estimates and 95% CIs of the HR for PFS across subgroups.

Estimates of ORR and DCR, along with its exact 95% CIs using the Clopper-Pearson method, will be computed for subgroup analyses.

The Kaplan-Meier estimation of median DOR and its 95% CIs will be presented by subgroup for participants who achieve an objective response.

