3.5.4	Summary of QTcB Interval (ms) From 12-Lead ECG	Safety	X	
3.5.5	Summary of QTcF Interval (ms) From 12-Lead ECG	Safety	X	
3.5.7	Summary of Heart Rate (bpm) From 12-Lead ECG	Safety	X	
3.5.8	Summary of Outliers of QT and QTcB and QTcF Interval Values From 12-Lead ECG	Safety	X	
3.5.9	Summary of Clinically Significant ECG Abnormality	Safety	X	

Figures

Figure No.	Title	DSMB
1.1	Kaplan-Meier Estimates of Progression-Free Survival by RECIST	
1.2	Forest Plot of Progression-Free Survival-TG2 vs TG1 by Subgroup	
1.3	Forest Plot of Progression-Free Survival-TG3 vs TG1 by Subgroup	
2.1	Kaplan-Meier Estimates of Duration of Response by RECIST	
2.2	Kaplan-Meier Estimates of Overall Survival	
3.1	Spider Plot of Percent Change from Baseline in Sum of Target Lesions	
3.2	Waterfall Plot of Best Percentage Change in Sum of Target Lesions	
3.3	Swimmer Plot of Overall Response and Duration of Treatment	
4.1	Line Graph of Selected Laboratory Values by Study Visit	X

Listings

Listing No.	Title	DSMB
2.1.1	Participant Enrollment and Disposition Status	X
2.2.1	Protocol Deviations	
2.2.2	Participant Inclusion and Exclusion Criteria Violations	
2.3.1	Analysis Populations	X
2.4.1	Demographic and Baseline Characteristics	X
2.4.2	Baseline Disease Characteristics and Disease History	X

Listing No.	Title	DSMB
2.4.3	Prior Radiation Treatment	
2.4.4	Prior Systemic Therapy	
2.4.5	Prior Surgery or Surgical Procedure	
2.4.7	Medical History	
2.4.8	Prior and Concomitant Medication	
2.5.1	Procedures and Nondrug Therapy	
2.5.2	Study Drug Administration	X
2.6.1	Deaths	
2.6.2	Best Overall Response, Duration of Response, and Progression-Free Survival	
2.6.3	Largest Percentage Reduction in Sum of Diameters of Target Lesions	
2.6.4	Overall Response Assessment by Visit	
2.6.5	Response Assessment: Target Lesions	
2.6.6	Response Assessment: Nontarget Lesions	
2.6.7	Response Assessment: New Lesions	
2.6.8	ECOG Status	
2.7.2	Adverse Events	X
2.7.3	Adverse Events Grade ≥ 3	X
2.7.4	Serious Adverse Events	X
2.7.5	Fatal Adverse Events	X
2.7.7.1	Adverse Events Leading to Interruption or Discontinuation of Study Drug	X
2.7.8.1	Immune-Related Adverse Events (Investigator-Assessed)	
2.7.8.2	Immune-Related Adverse Events (Sponsor-Assessed)	X
2.7.9.1	Infusion-Related Adverse Events (Sponsor-Assessed)	X
2.8.1	Clinical Laboratory Values - Hematology	X
2.8.2	Clinical Laboratory Values - Chemistry	X
2.8.3	Clinical Laboratory Values - Coagulation	
2.8.4	Clinical Laboratory Values - Urinalysis	

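### SAP 7.3.3 sets out to judge whether the PFS effect is consistent across subgroups, but plans only 36 within-category HRs with no comparison between categories, in subgroups that may be redrawn with no blinding or timing condition

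*SAP*

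**What the plan says.** SAP 7.3.3 states the aim as "To determine whether the treatment effect for the primary endpoint of PFS is consistent across various subgroups". The means is that "the estimated HR and its 95% CIs will be provided within each category of subgroup", from an unstratified Cox model, with the estimates and intervals shown on a forest plot.

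Eight factors are listed. Six have two levels (for example "Age: < 65 years, ≥ 65 years"; the others are sex, race, PD-L1 CPS, HPV p16 and LAG-3). Two have three levels: "Region: North America, EU, or Asia", and the number of target lesions. Appendix A plans a PFS forest plot for TG2 versus TG1 and another, "Forest Plot of Progression-Free Survival-TG3 vs TG1 by Subgroup".

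Two sentences make the set of subgroups flexible: "Subgroups may be further divided or combined based on emerging data", and "If the subgroup size is fewer than 5, then the analysis may not be conducted in this particular subgroup". The first carries no rule, date or blinding condition.

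Section 7.3.3 describes no treatment-by-subgroup comparison and does not say what pattern would count as inconsistent. Elsewhere, SAP 10.2 records that Amendment 1 removed type I error control because the study is not registrational. The text of Protocol 10.7 (Subgroup Analyses) is absent from the public copy.

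**The concern.** Consistency is a question about differences between categories. An HR and interval within one category answer a different question: whether there is an effect in that category, and how precisely it is estimated. Whether such an interval excludes 1 depends largely on how many events the category contains. Two categories with the same true effect can therefore easily fall on opposite sides of that line.

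LAG-3 and CPS are the factors most open to over-reading. Both are stratification factors, enrollment of LAG-3-low participants is capped at about 40% (SAP 3.1), and the scientific rationale rests partly on LAG-3 expression (Protocol 2.1.3). If the LAG-3-high interval excludes 1 and the LAG-3-low interval does not, readers may take this as selective benefit although the display has not tested that.

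Redrawing is a separate weakness. If categories are split or merged after treatment results are known, the displayed pattern may be partly chosen by the data. Appendix A also allows its list of displays to be modified without an SAP amendment where the nature of the analysis is unaffected, so a redrawn subgroup might not be recorded as post hoc.

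**Working it through.** **Reproducing the plan's figure.** With d events and 1:1 allocation, SE(log HR) = 2/√d. For d = 94 (SAP 3.2) this is 0.206, and |ln 0.6| = 0.511, so z = 2.476. Power at one-sided 5% is Φ(2.476 − 1.645) = 79.7% (SAP: 80.0%). At one-sided 10% it is Φ(2.476 − 1.282) = 88.4% (SAP: 88.4%). The approximation matches the plan.

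**Count of intervals.** 6 × 2 + 2 × 3 = 18 categories. Appendix A agrees: PFS tables 2.1.1.2 to 2.1.1.16 (15) and 2.1.1.18 to 2.1.1.20 (3). Two contrasts give 18 × 2 = 36. This is the listed number; categories with fewer than 5 participants may be dropped.

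**Chance that a 95% CI excludes 1 when HR = 0.6 everywhere.** Φ(|ln 0.6|·√d/2 − 1.96), with events in proportion to category share:

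| Share of sample | Events | CI excludes 1 |
|---|---|---|
| 100% | 94 | 70% |
| 60% | 56.4 | 48% |
| 50% | 47 | 42% |
| 40% | 37.6 | 35% |
| 20% | 18.8 | 20% |

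Take LAG-3 at 60/40 (the 40% is a cap, used here as an assumption). The chance that exactly one of the two intervals excludes 1, with identical effects, is 0.483 × (1 − 0.347) + (1 − 0.483) × 0.347 = 0.49 for a single contrast.

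**Whole display, by simulation.** Inputs from the documents: three arms of 54, control median 3 months, 12 months of enrollment, analysis at month 20, 1% annual dropout (Protocol Table 17; SAP 3.2). Exponential PFS was used, with HR 0.6 for both combinations in every subgroup, a shared control arm and unstratified Cox models. Participants without oropharyngeal cancer were left out of both p16 categories, as SAP 10.2 states. The simulated trials averaged 96 events per pair.

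Most subgroup shares are not in the documents and were assumed. Three sets were run with 1,500 trials each, the smallest category being 30%, 20% or 10% of participants and the factors independent.

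- Some intervals exclude 1 and others include it: 98% in all three sets. On average 65% to 67% of intervals include 1.
- At least one subgroup HR above 1: 64%, 76% and 89% in the three sets.
- At least one interval excludes the observed overall HR: 36% to 45%.

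**What a between-category comparison can deliver.** For a 50:50 factor, SE of the log ratio of HRs = √(4/47 + 4/47) = 0.413. The 95% CI extends by a factor exp(1.96 × 0.413) = 2.2 either way. For 80% power at two-sided 5%, the true ratio must be exp((1.96 + 0.842) × 0.413) = 3.2.

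**False signals from interaction tests.** 8 factors × 2 contrasts = 16 tests. If independent, 1 − 0.95^16 = 56% of uniform-effect trials show at least one p < 0.05. The simulated heterogeneity test gives 56% to 59%.

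**The case against.** The strongest reply is that the SAP never says an interval crossing 1 signals inconsistency, so the 98% criticises a rule the plan does not contain. Comparing subgroup intervals with the overall HR is an equally natural way to read a forest plot, and on that reading most uniform-effect trials (55% to 64%) show no discrepant interval. This stands. A reader might infer that a uniform effect will almost always look inconsistent; the documents do not support that, because the answer depends on a criterion the SAP leaves open. It also stands that the 98% mainly reflects low subgroup power: even the full 94-event comparison excludes 1 only 70% of the time.

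A reader might also infer that the plan fails to mark subgroup results as exploratory. That cannot be asserted. Protocol 10.7 cannot be read in the public copy, the only hypotheses (SAP 7.2) concern all participants, the primary p-value is itself nominal (SAP 7.3.2), and type I error control has been withdrawn. Section 7.3.3 simply carries no such label itself. Nor does any passage tie a subgroup result to a later decision.

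The sponsor and study team are blinded (Protocol 6.3) and no efficacy interim is planned (Protocol 10.5, SAP 9), which limits early redrawing. Neither says that redrawing must stop before unblinding.

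Finally, for two-level factors a reader could derive an approximate ratio from the printed HRs and intervals, since the categories do not overlap. That makes the remedy cheap. It does not make the planned display answer the stated question.

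**Conclusion.** The point holds as a modest methodological improvement. Section 7.3.3 asks whether effects differ between categories and supplies only estimates within them, and it leaves redrawing open with no blinding or timing condition. The count of 36 and the power figures follow from the documents. The display-level percentages rest on exponential PFS, independent factors and assumed subgroup shares. The 98% barely moves across the share sets, while the other readings range over 64% to 89% and 36% to 45%. The effect of redrawing cannot be quantified from the documents.

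The primary analysis is unaffected. A better comparison will not make this trial able to settle heterogeneity; it will show how little the trial can say about it.

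**What to change.** In SAP 7.3.3:

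- For each factor and contrast, estimate the treatment-by-subgroup ratio of HRs with its 95% CI from a Cox model and print it on the two forest plots. Name the reference category for region and number of target lesions. Treat the ratios as estimates; do not use unadjusted interaction p-values as a test of consistency.
- State that the subgroup results are descriptive and not adjusted for multiplicity.
- Allow categories to be split or merged only on blinded data before database lock, and mark any later change as post hoc.

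The cost is a few sentences, one extra model per factor and contrast (16 models), and an added column on each plot. The downside is imprecision: for an evenly split factor the interval runs about 2.2-fold either way, so heterogeneity can rarely be established or excluded. With 16 factor-by-contrast comparisons, some intervals will exclude 1 by chance, and the text should say so.

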7.3.4. Sensitivity Analyses

An additional sensitivity analysis of PFS will be done to assess the effect of errors in the stratification factors on the primary analysis. This sensitivity analysis will use the correct or actual values of the stratification factors in the analysis rather than using the stratification factors assigned at randomization. The sensitivity analysis will be done if more than 5% of participants have at least 1 error identified in the stratification factors assigned at randomization. The HR and 95% CI will be estimated based on the stratified Cox regression model using the actual values of the stratification factors for the log-rank test. Additionally, the HR and its 95% CI will be estimated based on the unstratified Cox regression model.

7.4. Analysis of the Secondary Efficacy Parameters

7.4.1. Best Overall Response and Objective Response Rate by RECIST

Best overall response for participants is the best response recorded postbaseline prior to and including the first PD, in the order of CR, PR, SD, PD, and NE determined by investigator assessment per RECIST v1.1.

The BOR will be determined from response assessments prior to or on the same day as new anticancer therapy. If any alternative cancer therapy is taken while on-study, then any subsequent assessments will be excluded from the BOR determination.

Best overall response for each participant is determined from the sequence of overall responses according to the following rules:

- CR = at least 2 consecutive determinations of CR at least 4 weeks apart before progression
- PR = at least 2 consecutive determinations of PR or better at least 4 weeks apart before progression (and not qualifying for a CR)
- SD = at least 1 SD assessment (or better) ≥ 6 months after start of treatment (and not qualifying for CR or PR)
- PD = meet progression criteria comparing with nadir (and not qualifying for CR, PR, or SD)
- NE = all other cases (ie, not qualifying for confirmed CR or PR and without SD after more than 7 weeks or PD)

In the case of SD, measurements must meet the SD criteria at least once after the date of first dose at a minimum interval of 6 months. Participants who fail to meet this criterion will have a

BOR of PD if the next available assessment after the initial assessment indicates PD, or a BOR of NE if there are no additional assessments available.

The largest percentage reduction in sum of diameters of target lesions will be listed. Spider plots (ie, percent change from baseline in sum of target lesions), waterfall plots (ie, best percentage change in sum of target lesions), and swimmer plots (ie, the overall response and duration of treatment) may be provided.

Objective response rate is defined as the proportion of participants with a CR or PR as BOR.

Estimates of ORR along with the exact 95% CIs using the Clopper-Pearson method will be computed for each treatment group.

Additionally, the difference of ORR between TG2 and TG1, between TG3 and TG1, and the corresponding 95% CIs for the difference using the Agresti-Caffo methods will be reported. This can be done using the SAS procedure PROC FREQ using the RISKDIFF option and selecting the Agresti-Caffo method for CIs. The common risk difference with the corresponding 95% CIs using the Newcombe method will be reported. This can be done using the SAS procedure PROC FREQ, adding IRT stratification factors in the analysis, using the COMMONRISKDIFF option and selecting the NEWCOMBE method for CIs.

Subgroup analyses for ORR will be performed as described in Section [7.3.3](#).

7.4.2. Disease Control Rate

Disease control rate is defined as the proportion of participants with a CR, PR, or SD (≥ 6 months) as the best objective response based on investigator assessment per RECIST v1.1.

Estimates of DCR along with the exact 95% CIs using the Clopper-Pearson method will be computed for each treatment group.

Additionally, the difference of DCR between TG2 and TG1, between TG3 and TG1, and the corresponding CIs for the difference using the Agresti-Caffo methods will be reported. This can be done using the SAS procedure PROC FREQ using the RISKDIFF option and selecting the Agresti-Caffo method for CIs. The common risk difference with the corresponding 95% CIs using the Newcombe method will be reported. This can be done using the SAS procedure PROC FREQ adding IRT stratification factors in the analysis, using the COMMONRISKDIFF option and selecting the NEWCOMBE method for CIs.

Subgroup analyses will also be performed for DCR as described in Section [7.3.3](#).

7.4.3. Duration of Response

Duration of response is a key secondary objective defined as the time from earliest date of disease response (CR or PR) until earliest date of disease progression as determined by investigator assessment per RECIST v1.1 or death from any cause, should the latter occur sooner than progression. Participants with no observed death or disease progression will be censored. Censoring for DOR will follow the same algorithm as censoring of PFS outlined in Section [7.3.2](#). If a participant meets multiple criteria for censoring, the censoring criterion that occurs earliest will be applied.

The Kaplan-Meier estimation of median DOR and its 95% CIs will be presented by treatment group for participants who achieve an objective response.

Subgroup analyses will also be done for DOR as described in Section [7.3.3](#).

[figure not shown]
7.4.4. Overall Survival

Overall survival is defined as the time from the date of randomization to the date of death due to any cause. Participants without documented death at the time of analysis will be censored at the date of last known contact.

- Kaplan-Meier curves, medians, and 95% CIs of the medians will be presented for each treatment group. The median follow-up time for OS will be calculated using reverse Kaplan-Meier methodology.

The HR for OS will be calculated, along with its 95% CI, from a stratified Cox model using the same stratification factors as the log-rank test, using Efron's likelihood approximation to account for ties in event times.

7.5. Analysis of Exploratory Efficacy Variables

8. SAFETY AND TOLERABILITY

[Appendix A](#) provides a list of planned data displays. Sample data displays are included in a separate document.

8.1. General Considerations

Summary tables may be replaced with listings when appropriate. For instance, an AE frequency table may be replaced with a listing if it only contains a few unique PTs reported on relatively few participants.

8.2. Adverse Events

8.2.1. Adverse Event Definitions

All safety analyses will be conducted using the safety population.

A TEAE is any AE either reported for the first time, or worsening of a pre-existing event, after first dose of study drug until 90 days after the last dose of study drug. Analysis of AEs (as discussed below) will be limited to TEAEs, but data listings will include all AEs regardless of their timing in relation to study drug administration, flagging those that are not TEAE. For purposes of analysis, all AEs will be considered TEAEs unless the AE can unequivocally be defined as not treatment-emergent.

Adverse events will be tabulated by MedDRA SOC and PT. Severity of AEs will be graded using the NCI CTCAE v5.0 using Grades 1 through 5. The CTCAE reporting guidelines and grading details are available on the Cancer Therapy Evaluation Program website.

The subset of AEs considered by the investigator to be related to study drug will be considered to be treatment-related AEs. If the investigator does not specify the relationship of the AE to study drug, the AE will be considered to be treatment-related. The incidence of AEs and treatment-related AEs will be tabulated. In addition, serious TEAEs will also be tabulated

Any missing onset date, causality, or severity must be queried for resolution. Unresolved missing or partial dates will be handled using the rules described in Section 4.1.4. Unresolved missing causality and severity will be handled according to the following rules:

- An unresolved missing causality will be considered treatment-related.
- An unresolved missing severity will be identified as an unknown severity.

The number and percentage (%) of participants reporting any TEAEs, any serious TEAEs, any Grade 3 or higher TEAEs, any treatment-related TEAEs, any treatment-related serious TEAEs, any treatment-related Grade 3 or higher TEAEs, any fatal TEAEs, and any TEAEs leading to treatment interruption/discontinuation will be tabulated by MedDRA SOC and PT. Data listings will include all AEs regardless of their timing to study drug administration.

Infusion-related reactions, as well as irAEs, may be summarized separately.

